4.1.4 Pharmacokinetic Population

4.1.4.1 Ocular PK population

All patients who are included in the safety population and for whom quantified vitreous (ocular) concentration of ONL1204 is available will be included in the ocular PK population. Patients with protocol violations will be assessed on a patient-by-patient basis for inclusion in the ocular PK Population. Ocular PK Population determination will be made before database lock by the Study Pharmacokineticist. This ocular PK population will be used for the summaries and graphical presentation of ocular ONL1204 concentration data.

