1.3.2 Rationale for Pharmacokinetic testing

Systemic PK will be evaluated following IVT administration of ONL1204. ONL1204 is not expected to be detected in the plasma and this will be confirmed in this study, which will preclude additional systemic PK evaluation in future studies.

ONL1204 will also be measured in the vitreous samples taken at the time of the vitrectomy to evaluate clearance of the drug from the vitreous.

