Study Visit	Visit 1 Day 1 Baseline ² / Injection			Visit 2 Day 2 (¹ ,	Visit 3 (Day 4 +)	Visit 4	Visit 5	Visits 6, 7	Visit 8	Unscheduled Visit(s)
				1 day Post- Injection	3 + days Post- Injection) Day of Surgery (Vitrectomy) ³	1 Day Post- Surgery	14 Days (±4 days) Post- Surgery	Weeks 6, 9 (±7 days)	Week 24 (±14 days) Exit or early termination	
Assessment	Pre- Injection	Study Drug IVT	Post- Injection							
Blood Sampling for Plasma ONL1204 PK			X ⁵	X	X		X	X ⁶	X	
Study Drug IVT		X								
Pin Hole Visual Acuity						OU				
Low Luminance ETDRS Best Corrected Visual Acuity								OU	OU	
Low Contrast ETDRS Best Corrected Visual Acuity								OU	OU	
Contrast Sensitivity Testing								OU	OU	
Farnsworth D15 Color vision test									OU	

⁵ Post-injection blood sample for plasma PK to be drawn 1 hour (\pm 15 minutes) after study drug IVT. ⁶ Blood sample for plasma PK to be drawn only on Visit 7 (week 9)

Page 27 of 52

Study Visit Visit 1 Visit 2 Visit 3 Visit 4 Visit 5 Visits 6, 7 Unscheduled Visit 8 Day 2 (¹, Day 1 (Day 4 +) Visit(s) Baseline²/ Injection 3 + days Post-1 day 1 Day Post-Week 24 14 Days Weeks 6, 9 (±7 Injection) (±14 days) Post-Surgery (±4 days) days) Injection Day of Post-Exit or early Surgery Surgery termination (Vitrectomy)³ Pre-Study Post-Assessment Injection Drug Injection IVT Intraocular SE⁴ OU OU SE OU OU OU OU Pressure⁷ Slit Lamp SE⁴ OU OU OU SE OU OU Biomicroscopy Indirect SE⁴ OU OU OU SE OU OU Ophthalmoscopy Fundus OU OU Photography **ONL1204** Fundus OU Autofluorescence B Scan SE Ultrasonography (optional) SD OCT OU OU SE SE

Note: Screening procedures are in red

Abbreviations: AE = Adverse event; ETDRS = Early Treatment Diabetic Retinopathy Study; IOP = Intraocular pressure; PK = Pharmacokinetic;

Post-op = Postoperative; OU = Both eyes; SD OCT = Spectral Domain Optical Coherence Tomography; SE = Study eye; UA = Urine analysis.

⁷ iCare Tonometry and Tonopen methods of measurement are acceptable.

Page 28 of 52

Study Visit	Visit 1 Day 1			Visit 2 Day 2 (¹ ,	Visit 3 (Day 4 +)	Visit 4	Visit 5	Visits 6, 7	Visit 8	Unscheduled Visit(s)
	Baseline ² / Injection			1 day Post- Injection	3 + days Post- Injection) Day of Surgery (Vitrectomy) ³	1 Day Post- Surgery	14 Days (±4 days) Post- Surgery	Weeks 6, 9 (±7 days)	Week 24 (±14 days) Exit or early termination	
Assessment	Pre- Injection	Study Drug IVT	Post- Injection							
Vitreous Tap for Cytokine / Biomarker Analysis	SE									

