9.1.3.2 Ocular PK Population

The ocular PK Population will comprise all patients in the Safety Population who provide adequate ocular PK samples to calculate the PK parameters. Patients with protocol violations will be assessed on a patient-by-patient basis for inclusion in the ocular PK Population. The PK analysis will be conducted using the ocular PK Population.

For the pharmacokinetic data, per cohort and per protocol analyses will be performed. Each cohort population is defined as all patients within a dose cohort who received their assigned treatment and includes all those with no major protocol deviations. The per protocol population is defined as all patients who received their assigned treatment and includes all those with no major protocol deviations. These populations will be determined well before database lock. If patients withdraw from the study, their plasma concentration data may be included in the pharmacokinetic analysis provided there are no significant protocol noncompliance issues.

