- f. The specific reasons for 'not calculable (NC)' and 'not reported (NR)' for PK parameters will be provided as footnotes in the PK results listings and summaries.

For vitreous concentration-time data/profiles the following will be applied:

- a. Concentrations that are below limit of quantification (BLQ) prior to the dosing (Pre-dose) will be set equal to zero. Post dose BLQ concentrations will be set to zero.
- b. Where there are no results, these will be set to missing.

c. If more than 75% of values per nominal timepoint and treatment group are BLQ, then all descriptive statistics, except for nBLQ, will be denoted as not calculable (NC).

Conversion of categorical values

In some instances, continuous variables are expressed as a range (i.e., < 10). In such cases, values may be converted to the range boundary (upper or lower limit as applicable). As an example, a value of <10 may be converted to 10. Such substitutions will be clearly documented in the footnotes of relevant outputs.

Coding of Events and Medications

Medical history and AE verbatim terms will be coded using the Medical Dictionary for Regulatory Activities (MedDRA) using version 23.0. Terms will be coded to the full MedDRA hierarchy, but the system organ class (SOC) and preferred terms (PT) will be of primary interest for the analysis.

Prior and concomitant medications will be coded using the World Health Organization Drug Dictionary using the latest version available at the time of study commencement. Medications will be mapped to the full WHO-DD Anatomical Therapeutic Chemical (ATC) class hierarchy, but PTs will be of primary interest in this analysis.

Treatment Groups

- Cohort 1 ONL1204 25 μg
- Cohort 2: ONL1204 50 µg
- Cohort 3 ONL1204 100 μg
- Cohort 4 ONL1204 200 μg
- Overall

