10.4 Ocular PK analysis

An undiluted vitreous sample will be collected at the time of vitrectomy to assess ONL1204 drug levels. A separate summary and listing will be provided for the same. Considering the sampling limitations, no ocular PK analysis will be applicable for this study and hence concentration listings and summaries along with figures will be provided based on ocular PK population.

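### By requiring a *quantified* vitreous level, the SAP as worded drops BLQ eyes from the vitreous summaries and figures, contradicts its own vitreous BLQ rules, and would overstate residual drug if any eye is BLQ

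*SAP*

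**What the plan says.** **Population.** SAP 4.1.4.1 includes Safety Population patients "for whom quantified vitreous (ocular) concentration of ONL1204 is available will be included in the ocular PK population". Patients with protocol violations are considered case by case, but no clause admits a BLQ result. The section adds: "This ocular PK population will be used for the summaries and graphical presentation of ocular ONL1204 concentration data".

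**Outputs.** SAP 10.4 drops ocular PK parameters because of the limited sampling and says that "concentration listings and summaries along with figures will be provided based on ocular PK population".

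**Sampling.** SAP 10.4 describes a single drug-level sample: "An undiluted vitreous sample will be collected at the time of vitrectomy to assess ONL1204 drug levels". In Protocol Table 4-1 the baseline procedure is labelled "Vitreous Tap for Cytokine / Biomarker Analysis", with no drug assay.

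**BLQ handling.** SAP section 3 (Handling of Missing Data) has a rule set specifically for vitreous data. It states: "Post dose BLQ concentrations will be set to zero". It also says that when more than 75% of values at a time point in a treatment group are BLQ, every statistic except the BLQ count becomes not calculable. Under General Considerations, PK concentration summaries are to show the number of BLQ values, the geometric mean and the geometric CV%.

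**Purpose and protocol definition.** Protocol 1.3.2 says that drug is measured in vitreous samples "taken at the time of the vitrectomy to evaluate clearance of the drug from the vitreous". Protocol 9.1.3.2 defines the ocular PK population as "all patients in the Safety Population who provide adequate ocular PK samples to calculate the PK parameters".

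**The concern.** Membership of the population depends on the outcome that the population is meant to summarize. With one sample per patient, a BLQ result leaves no other vitreous value to keep the patient in. The eyes that have cleared most drug are the ones removed, although clearance from the vitreous is the stated reason for taking the sample.

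The SAP also contradicts itself. It gives rules for vitreous BLQ values, then places the summaries and figures on a population that, as worded, contains none. A reader would see zero BLQ results in every cohort and could not tell from the table whether that was an observation or a consequence of the definition.

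At stake is a descriptive picture of residual vitreous drug by dose. Under the exploratory objective (Protocol 2.2, SAP 2.1.3), the ocular fluid results help inform Phase 2 dose selection.

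**Working it through.** The plan states no figure on this point, so there is none to reproduce. The check is logical first, then arithmetical.

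**Inputs**
- Cohort size n = 4, 16 overall (Protocol, Study Schematic).
- One vitreous drug-level sample per patient (SAP 10.4; Protocol Table 4-1).
- Vitreous BLQ set to zero, and the more-than-75% rule (SAP section 3).
- Lowest dose 25 µg and human vitreous volume about 4,400 µL (Protocol 1.3.1).
- Surgery 3 or more days after injection (Protocol 4.1), planned within 7 days (Protocol 1.2.1).
- Vitreous LLOQ: not given. The only LLOQ stated is 1 ng/mL for rabbit plasma (Protocol 1.2.1). I assume 1 to 100 ng/mL for vitreous.

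**Step 1: can the BLQ rules operate?** If only quantified results enter, the BLQ count in each summary is 0 by construction and the zero rule has no value to act on. For n = 4, 3/4 is exactly 75%, so more than 75% requires 4 of 4. That case leaves no patient in the cohort, so the rule cannot trigger.

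**Step 2: size relative to the SAP's zero rule.** Let S be the sum of the quantified levels and k the number of BLQ eyes. The mean with BLQ set to zero is S/n. The mean over quantified eyes is S/(n−k). The ratio is n/(n−k), whatever the quantified levels are.

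| BLQ eyes of 4 | Ratio of means | BLQ count shown | Actual BLQ count |
|---|---|---|---|
| 0 | 4/4 = 1.00 | 0 | 0 |
| 1 | 4/3 = 1.33 | 0 | 1 |
| 2 | 4/2 = 2.00 | 0 | 2 |
| 3 | 4/1 = 4.00 | 0 | 3 |
| 4 | cohort empty | 0 | 4 |

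For the SAP's Overall group, 1 BLQ eye of 16 gives 16/15 = 1.07.

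**Step 3: size relative to the true mean.** A BLQ level lies between zero and the LLOQ, so the true mean is at least S/n. The overstatement of the true mean is therefore at most n/(n−k). It still exceeds 1 whenever k is 1, 2 or 3, because every quantified level is at or above the LLOQ. Illustration with assumed levels: three eyes at 2 × LLOQ and one at 0.9 × LLOQ have a true mean of (6 + 0.9)/4 = 1.725 × LLOQ. The quantified-only mean is 2 × LLOQ. The ratio is 2/1.725 = 1.16, against the bound of 1.33.

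**Step 4: how likely is a BLQ eye?** Assume even mixing in 4.4 mL and first-order loss. At 25 µg the starting level is 25,000 ng / 4.4 mL ≈ 5,682 ng/mL. The number of half-lives to the LLOQ is log2(5,682/LLOQ).

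| Assumed LLOQ | Half-lives to LLOQ | Half-life needed for BLQ by 3 days (72 h) | By 7 days (168 h) |
|---|---|---|---|
| 1 ng/mL | 12.47 | below 5.8 h | below 13.5 h |
| 100 ng/mL | 5.83 | below 12.4 h | below 28.8 h |

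Protocol 1.2.1 and 1.4.1 describe slow ocular elimination, with most drug still in the eye at surgery. Half-lives this short would run against that expectation. On the other side, if each eye had an assumed 5% chance of being BLQ, the chance of at least one among 16 would be 1 − 0.95^16 = 56%; at 10% it would be 1 − 0.90^16 = 81%. The documents do not fix this probability.

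**Step 5: a gap behind the contradiction.** Once BLQ eyes are admitted and set to zero, the vitreous geometric mean and geometric CV% cannot be computed, because the logarithm of zero is undefined. Protocol 9.3.1.7 sets BQL values to missing for these statistics, but only under systemic PK. The SAP gives no vitreous rule.

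**The case against.** **The word may mean assayed.** Elsewhere in section 3 (the baseline definition and the plasma parameter rules) the SAP uses *quantifiable* for a value above the limit. *Quantified* and available could mean only that an assay result exists, and the vitreous BLQ rules make sense only on that reading. This is plausible as intent, and on that reading nothing is lost. But the text does not say so, and population membership is decided from this text.

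**BLQ eyes may not occur.** The protocol expects drug to persist to surgery, and Step 4 shows how short the half-life would have to be. This stands: a reader might infer that residual drug *is* overstated, and the documents do not support that. However, this is a first-in-human study, and the nonclinical expectation is what the sample should test.

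**The fold-changes are not the bias.** Correct. They compare with the zero rule, and the 2-fold and 4-fold rows need several BLQ eyes, which no document predicts.

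**Exclusions would be visible elsewhere.** SAP 5.1.2 counts and lists membership of each population. SAP 4.1.1 puts all listings on the ITT population. Section 3 lists sampling times for patients with concentration data even when they are excluded from the PK population. So it would be too strong to say that a BLQ eye vanishes, or that the BLQ rules can never act anywhere. The claim holds for summaries and figures. For listings, these provisions pull against SAP 10.4, which names the ocular PK population.

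**The protocol definition is not plainly inclusive.** It ties adequate samples to calculating PK parameters, which one vitreous sample cannot support. It does not require a quantified level, but it cannot be read as clearly admitting BLQ eyes.

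**The consequence is limited.** SAP 10.4 estimates no ocular PK parameters, and no hypothesis test is planned. That clearance would look slower, or that doses would be distorted unequally, is a reader's inference from a descriptive table.

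**Conclusion.** The concern stands as an internal contradiction with a conditional bias. On its plain wording, SAP 4.1.4.1 removes any BLQ eye from the vitreous summaries and figures, where section 3's vitreous BLQ rules and BLQ count then cannot operate. If 1, 2 or 3 of 4 eyes in a cohort are BLQ, the mean is overstated by at most 1.33-, 2- or 4-fold, and the table shows no BLQ results. If all 4 are BLQ, the cohort is empty, so complete clearance would look like absent data; the section 3 rule would have shown a BLQ count of 4 and nothing else.

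This rests on reading *quantified* as not BLQ and on one drug-level sample per patient. The number of BLQ eyes is unknown and may be zero, in which case the summary is unbiased. The endpoint is exploratory and descriptive, and the vitreous summary is not among the primary safety endpoints. The wording should be corrected, but it does not threaten the trial's main conclusions.

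**What to change.** Redefine the ocular PK population in SAP 4.1.4.1 as all Safety Population patients with a reported vitreous ONL1204 result from the vitrectomy sample, including results reported as BLQ. If *quantified* was meant as assayed, this wording says so. The existing case-by-case review of protocol violations can stay.

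Then:
- Show the number BLQ over the number assayed for each cohort beside the vitreous summary.
- State how BLQ values enter the vitreous geometric mean and geometric CV%, since the zero rule makes them incalculable.
- Settle which population the vitreous listings use, because SAP 4.1.1 and 10.4 differ.
- Record the departure from Protocol 9.1.3.2 in SAP section 15, which currently declares no changes to the planned analysis.

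The cost is one sentence for the definition and a few lines of clarification. It needs no new samples, assays or visits. The change should be made before the ocular PK population is determined, which the SAP places before database lock.

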4.1.4.2 Plasma PK population

For the systemic PK data, per cohort and per protocol analysis will be performed. All patients who are included in the safety population with no major protocol deviations, who provide adequate PK samples and have a sufficient PK profile that allows the calculation of relevant PK parameters will be included in the PK population.

Plasma PK population is defined as all patients who are included in the safety population and for whom an evaluable plasma concentration-time profile of ONL1204 is available for the determination of at least one of the PK parameters among C_{max} , T_{max} and AUC_{0-t} with no major protocol deviations that could potentially affect the PK profile.

Plasma PK population determination will be made before database lock by the Study Pharmacokineticist.

The plasma PK population will be used for the plasma PK analysis, the summaries and graphical presentation of all plasma PK data.

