- Actual Time from First Dose (hours) = (Date/Time of First Dose PK Sample collection) (Date/Time of First Dose)
- Actual Time Deviation (hours) = (Actual PK Sample Collection Time Post Dose) (Scheduled PK Sample Collection Time Post Dose).
- Treatment Emergent Adverse Events (TEAEs) are defined as adverse events that occurred following the first administration of study medication.

Inferential Analyses

Descriptive statistics will be used to summarize the safety, PD and PK data. No formal hypothesis testing is planned.

Multiple Comparisons and Multiplicity Adjustments.

Not applicable for this study.

Handling of Missing Data

For the classification of Treatment emergent adverse event (TEAE) and Concomitant medication, the following will be applied in the following order:

- a. If all dates/times (start and stop) missing, the event/medication will automatically be classified as a TEAE/Concomitant medication.
- b. For AEs with a missing start date/time, if the event end date/time is prior to first study drug administration, the event will not be classified as a TEAE.
- c. If only the AE start year/ medication end year is present and is the same or is after the first study drug administration year unit, the event/medication will be classified as a TEAE/Concomitant medication.
- d. If the AE start month and year/medication end month and year are present and are the same or after the first study drug administration month and year units, the event/medication will classified as a TEAE/Concomitant medication.

For plasma concentration-time data/profiles and PK analysis the following will be applied:

- a. Concentrations that are below limit of quantification (BLQ) prior to the dosing (Pre-dose) will be set equal to zero. Post dose BLQ concentrations will be set to zero.
- b. Where there are no results, these will be set to missing.
- c. If more than 75% of values per nominal timepoint and treatment group are BLQ, then all descriptive statistics, except for nBLQ, will be denoted as not calculable (NC).
- d. For the purpose of calculating the non-compartmental plasma PK parameters, concentrations that are BLQ prior to the first quantifiable value will be set equal to zero and BLQ values after measurable concentrations will be set to zero.
- e. For the calculation of summary statistics of plasma PK parameters, all NR (not reported) and NC (not calculable) values in a data series will be set to missing.

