10. PHARMACOKINETICS

10.1 Plasma PK Analysis

The plasma PK samples for ONL1204 will be at specified times as follows:

- ٠
- Post-intravitreal injection
- 1-day post- intravitreal injection
- 3+ days post- intravitreal injection or day of surgery (vitrectomy)
- 14 days post-surgery
- Week 9
- Week 24 exit or early termination

All PK summary tables will be based on the plasma PK population. All analyses will be summarized as described in section 3.1 (PK - continuous descriptive analysis). All listings will be based on the safety population.

The following pharmacokinetic parameters will, where possible, be determined from the plasma concentrations of ONL1204 by non-compartmental method using Phoenix WinNonlin[®] software (Version 8.3 or higher):

Pharmacokinetic Parameters of Plasma ONL1204 Following a Single Dose Administration of ONL1204 Intravitreal Injection

Parameter	Definition
AUC0 last	The area under the plasma concentration time curve, from time 0 (time of dosing)
	to the last time point with measurable analyte concentration, calculated by the log
	down, linear up trapezoidal method
AUC0 inf	The area under the plasma concentration time curve from time 0 extrapolated to
	infinity. AUC0 inf is calculated as the sum of AUC0 last plus the ratio of the last
	measurable plasma concentration to the elimination rate constant (λz).
Cmax	Maximum analyte plasma concentration
Tmax	Time to maximum observed analyte concentration. If the maximum value occurs
	at more than one time point, Tmax is defined as the first time point with this
	value.
t ¹ /2	Apparent plasma terminal elimination half life calculated as $\ln (2)/\lambda z$

Parameter	Definition		
C _{max}	Maximum concentration which is directly determined from the plasma		
	concentration time profiles		
T _{max}	Time to maximum concentration. If the same C _{max} concentration occurs at		
	different time points, T _{max} is assigned to the first occurrence of C _{max} .		
AUC _{0-last}	Area under the drug concentration-time curve, from time zero to the last		
	measurable concentration using the 'Linear Up and Log Down' method		
AUC _{0-inf}	Area under the drug concentration-time curve, from time zero to infinity (∞) using		
	the following formula		
	$AUC_{0-\infty} = AUC_{0-t} + \frac{C_{t}}{\lambda_{z}}$		
	Where, C'_t is the observed concentration at the time t (last time point with a		
	measurable plasma concentration above the quantification limit) at which		

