18. TABLES

Table Number	Table Title	Population
14.1	Demographics and Other Baseline Characteristics	
14.1.1	Summary of Subject Enrolment and Disposition	ITT
14.1.2	Demographics and Baseline Characteristics	ITT
14.2	PK/PD	
14.2.1	Plasma ONL1204 Concentrations (unit) by Treatment and Time	РК
14.2.2	Plasma ONL1204 Pharmacokinetic Parameters by Treatment	РК
		РК
14.3	Safety	
14.3.1	Concomitant Medication by ATC Classification	Safety
14.3.3	Adverse Events	
14.3.3.1	Summary of Overall Treatment Emergent Adverse Events	Safety
14.3.3.2	Incidence of Ocular Treatment-Emergent Adverse Events by SOC and PT	Safety
14.3.3.2a	Incidence of Non-Ocular Treatment-Emergent Adverse Events by SOC and PT	Safety
14.3.3.3	Incidence of Serious Ocular Treatment-Emergent Adverse Events by SOC and PT	Safety
14.3.3.3a	Incidence of Serious Non- Ocular Treatment-Emergent Adverse Events by SOC and PT	Safety
14.3.3.4	Incidence of Ocular Treatment-Emergent Adverse Events by SOC, PT and Maximum Severity	Safety
14.3.3.4a	Incidence of Non-Ocular Treatment-Emergent Adverse Events by SOC, PT and Maximum Severity	Safety
14.3.3.5	Incidence of Ocular Treatment-Emergent Adverse Events by SOC and PT and relationship to study drug	Safety
14.3.3.5a	Incidence of Non-Ocular Treatment-Emergent Adverse Events by SOC and PT and relationship to study drug	Safety
14.3.3.6	Incidence of Ocular Treatment-Emergent Adverse Events by SOC and PT and relationship to procedure	Safety
14.3.3.6a	Incidence of Non-Ocular Treatment-Emergent Adverse Events by SOC and PT and relationship to procedure	Safety
14.3.4	Laboratory Parameters	
14.3.4.1	Hematology Results - Change of Hematology Values	Safety
14.3.4.2	Hematology Results – Normal/Abnormal Shift Table	Safety
14.3.4.3	Chemistry Results - Change of Chemistry Values	Safety
14.3.4.4	Chemistry Results – Normal/Abnormal Shift Table	Safety
14.3.5	Other Safety	
14.3.5.1	Vital Signs - Values and Change from Baseline	Safety
14.3.6.1	Summary of Best Corrected Visual Acuity (BCVA) (Letters)	Safety

Novotech – Strictly Confidential

2022-09-14

Table Number	Table Title	Population
14.3.6.2 14.3.6.3 14.3.6.4 14.3.6.5 14.3.6.6	Summary of Best Corrected Visual Acuity (BCVA) (LogMAR Values) Summary of Low Luminance and Low Contrast BCVA Indirect Ophthalmoscopy Summary of Biomicroscopy Examination Summary of Intraocular Pressure (mmHg)	Safety Safety Safety Safety Safety Safety
14.3.6.7 14.3.6.8	Summary of Pin Hole Visual Acuity Summary of Log Contrast Sensitivity Scores	Safety Safety

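### The SAP leaves open whether a patient with only BLQ plasma values enters the plasma PK population, so Table 14.2.1 may be unable to show the non-detection the protocol expects; separately, setting BLQ to zero breaks the planned geometric mean

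*SAP*

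**What the plan says.** SAP 4.1.4.2 defines the plasma PK population twice. The first definition asks for patients without major deviations who give adequate samples and "have a sufficient PK profile that allows the calculation of relevant PK parameters will be included in the PK population". The second takes Safety-population patients "for whom an evaluable plasma concentration-time profile of ONL1204 is available for the determination of at least one of the PK parameters", naming AUC, Cmax and Tmax as the candidates, again without major deviations affecting the profile. Neither mentions a patient with no quantifiable value.

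The section continues: "The plasma PK population will be used for the plasma PK analysis, the summaries and graphical presentation of all plasma PK data". SAP 10.1 agrees: "All PK summary tables will be based on the plasma PK population". In SAP section 18 the concentration table, 14.2.1 ("Plasma ONL1204 Concentrations (unit) by Treatment and Time"), carries the PK population label.

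The plasma rules in SAP section 3, Handling of Missing Data, bear on this as follows:

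- Rule a: "Post dose BLQ concentrations will be set to zero".
- Rule c: "If more than 75% of values per nominal timepoint and treatment group are BLQ", every statistic except the BLQ count is shown as not calculable (NC).
- Rule d, for PK parameters: "concentrations that are BLQ prior to the first quantifiable value will be set equal to zero". It does not cover a profile with no quantifiable value.

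The General Considerations in the same section ask for a geometric mean and geometric CV% of concentrations.

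The protocol differs. Section 9.3.1.7 requires counts and percentages of BLQ values at each time point and sets BLQ to missing for the geometric mean and geometric CV%. It sits under section 9.3.1, which uses the Safety Population. Section 9.1.3.2 defines PK sets by assigned treatment and absence of major deviations. SAP section 15 records no change to the planned analysis.

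**The concern.** Protocol 1.3.2 says the drug is not expected in plasma, that the study will confirm this, and that confirmation will remove the need for systemic PK work in later studies. Protocol 1.2.1 reports undetectable rabbit plasma at a total dose equal to the planned top human dose. The all-BLQ patient is therefore the expected patient, and the population that feeds the summary table is defined by a condition that such a patient seems to fail. If so, the table keeps only patients with detectable drug. It is then empty when the protocol's expectation is met, and overstates detection when it is partly met.

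The geometric-mean point is independent. A geometric mean needs positive values, and the SAP replaces BLQ by zero without the exception that the protocol makes for this statistic.

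**Working it through.** The documents give no figure of their own to reproduce here. The check has three parts.

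**1. Can an all-BLQ patient qualify under SAP 4.1.4.2?**

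- AUC: SAP 10.1.1.4 needs at least three consecutive values above the LLOQ. Not met.
- Cmax and Tmax: these could be read as Cmax = 0 at the first sample, since BLQ is set to zero and SAP 10.1 assigns a tied Tmax to its first occurrence. The SAP does not say that this makes a profile evaluable, and rule d presupposes a quantifiable value.

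So there are two readings. Exclusion is the natural one; inclusion is possible.

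**2. What Table 14.2.1 shows**

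Inputs: 16 patients in 4 cohorts of 4 (Protocol, Study Schematic and 4.1); six post-dose plasma times, namely 1 hour, Day 2, day of surgery, 14 days post-surgery, Week 9 and Week 24 (Protocol Table 4-1; SAP 10.1). Complete sampling is assumed.

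*Nothing detected.* Cells: 4 × 6 = 24. Planned results: 16 × 6 = 96. Exclusion gives n = 0 in all 24 cells. Inclusion gives n = 4, nBLQ = 4 in each, that is 16/16 BLQ at each time.

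*k of 4 patients in a cohort quantified at 1 hour, the others BLQ at all times (assumed).* Exclusion leaves n = k and nBLQ = 0. Inclusion gives n = 4 and nBLQ = 4 − k. With S the sum of the quantified values, the means are S/k and S/4 (BLQ as zero), so their ratio is 4/k.

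| k | Detected, inclusion | Detected, exclusion | Ratio of means |
|---|---|---|---|
| 1 | 1/4 = 25% | 1/1 = 100% | 4.00 |
| 2 | 2/4 = 50% | 2/2 = 100% | 2.00 |
| 3 | 3/4 = 75% | 3/3 = 100% | 1.33 |

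*Overall group (if shown), 1 of 16 quantified.* Inclusion: 15/16 = 93.75% BLQ, above 75%, so NC with nBLQ = 15. Exclusion: 0/1 BLQ, so a mean is printed from one patient. The 75% rule never sees the 15 BLQ values it was written for.

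**3. Geometric mean with BLQ set to zero**

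The geometric mean is exp(mean of ln x), and ln 0 is undefined; taken as the root of a product, it is 0. The geometric CV% is undefined.

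| Group size | Valid | Zero or undefined | NC under the 75% rule |
|---|---|---|---|
| 4 | nBLQ = 0 | nBLQ = 1, 2, 3 (3/4 is exactly 75%, not more) | nBLQ = 4 |
| 16 | nBLQ = 0 | nBLQ = 1 to 12 (12/16 = 75%) | nBLQ = 13 to 16 |

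Illustration with assumed values 1.2, 1.5 and 2.0 ng/mL plus one BLQ: under the SAP the product is 0 and the statistic is zero or undefined; under Protocol 9.3.1.7 it is (1.2 × 1.5 × 2.0)^(1/3) = 3.6^(1/3) = 1.53 ng/mL with n = 3.

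If each value is BLQ independently with probability p (assumed), the chance that a cohort-time cell of 4 falls in the failing range is 1 − (1 − p)^4 − p^4: 0.68, 0.88, 0.68 and 0.34 for p = 0.25, 0.5, 0.75 and 0.9.

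**The case against.** The best counter-argument is that the SAP, read as a whole, supports inclusion. One parameter is enough, zero substitution yields Cmax = 0 mechanically, and a 75% rule that in a cohort of 4 fires only at 4/4 suggests that all-BLQ rows were foreseen. The study pharmacokineticist also decides the population before database lock, so exclusion is not automatic. This shows that the text is open, not that it is settled: all-BLQ rows also arise at late times among patients quantified earlier. Inclusion would also move the problem to Table 14.2.2. SAP 10.1 withholds the terminal-phase parameters when there is no log-linear phase, but Cmax and Tmax are not on that list. The phrase limiting parameters to where they are possible, and the NC and not-reported conventions, soften this risk without clearly removing it.

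Second, the data are not lost. Listing 16.2.6.1 is on the Safety population, and SAP 5.1.2 reports the size of each population and each patient's inclusion. This stands and limits the harm to summaries and plots. A reader would still have to rebuild the BLQ counts by hand.

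Third, the protocol itself is not of one mind. The Safety Population for plasma follows from where section 9.3.1.7 sits, plasma levels are listed as exploratory, and section 9.1.3.2 excludes major deviations. That stands too, but neither protocol set drops a patient for being BLQ.

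Fourth, the ratios of means are measured against a mean with BLQ as zero and need the remaining patients to be BLQ at every time; the geometric-mean failure needs mixed detection. Both are true and are stated as assumptions here. One PK row in SAP section 18 has lost its title in the text available, so 14.2.1 is the only titled plasma concentration table that can be seen.

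**Conclusion.** The concern holds, in two independent parts.

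The population rule is silent on the outcome the protocol expects. Under exclusion, which is the natural but not the certain reading, complete non-detection gives an empty Table 14.2.1, and partial detection shows 100% detected where the true figure is 25%, 50% or 75%. Under inclusion the table works and the remaining risk is Cmax = 0 entering Table 14.2.2.

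The conflict over geometric statistics exists on either reading. It produces an unusable value for 1 to 3 BLQ of 4, or 1 to 12 of 16, in place of a workable protocol rule that the SAP drops without recording a change.

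Plasma PK is exploratory, no hypothesis is tested and no primary endpoint is affected. The matter should be corrected because later systemic PK work is to be forgone on the strength of this result. Confidence is medium, since the first part depends on how the definition is read.

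**What to change.** 1. Base plasma concentration summaries, plots and BLQ counts and percentages, by cohort and time point, on treated patients with at least one assayed post-dose sample, BLQ or not. State how this set relates to Protocol 9.1.3.2 and to 9.3.1 with 9.3.1.7.
2. Keep the evaluable-profile condition for Table 14.2.2 only. State there that all-BLQ profiles are not calculable, and report how many there were.
3. Restore the protocol rule that BLQ is missing for the geometric mean and geometric CV%, and print the n used.
4. Record any remaining departure from the protocol in SAP section 15.

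If no patient is ever quantified, Table 14.2.1 would then show 16/16 BLQ at each time. The exact two-sided 95% upper limit for 0/16 ever detected is 1 − 0.025^(1/16) = 20.6%, which also shows how much the study can confirm.

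In SAP 4.1.4.1, replacing quantified by assayed for vitreous samples is a minor wording correction with little expected effect.

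Cost: SAP wording and a changed population flag for the plasma concentration tables and figures. No new data.
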